4. TREATMENT PLAN

4.1 Phase I

Three dose levels of lenalidomide (10 mg, 15 mg, 20 mg) will be evaluated with a fixed dose of obinutuzumab (1000mg) as outlined in Table 1. (obinutuzumab will be given in divided doses on cycle 1; 100mg IV on day 1, and 900mg IV on day 2, subsequent doses will be given over 1 day) Up to 18 patients may participate in the Phase I component of the study, depending on the level at which toxicity is observed. Subjects will be assigned to a dose level based on the order of study entry and toxicities seen in prior patients. The dose escalation process is described below. There will be no intra-patient dose escalation. DLT will be assessed during the first course of each cohort (28 days), and refers to a medically significant event which meets criteria using National Cancer Institute Common Terminology Criteria for Adverse Events (NCI CTCAE) version 4. (see section 2.3.2)

Table 1. Dose levels to be tested in phase I portion

Dose Level	Lenalidomide Dose (days 2-22 followed by 6 days of no therapy)	Obinutuzumab dose
-1	5 mg	1000mg IV
1	10 mg	
2	15 mg	
3	20 mg	

4. 2 Phase II

Additional pts will be enrolled into two cohorts at the recommended dose level (MTD) established in Phase I up to a maximum of 30 patients each in two independently enrolling cohorts.

Cohort A: 30 patients with relapsed/refractory follicular lymphoma

Cohort B: 30 patients follicular lymphoma, marginal zone lymphoma or SLL

[figure not shown]
4. 3 Treatment Schedule

Lenalidomide capsules will be taken orally daily each day on days 2 - 22, followed by 6 days of no therapy of each 28-day cycle. Obinutuzumab will be given by intravenous infusion on day 1,,2, 8, 15, and 22 of cycle one and on day 1 of each subsequent cycle up to 6 cycles. Patients who do not progress following 6 cycles and are deriving benefit from the combination in the opinion of the treating physician can receive further cycles of combination up to 12 cycles of lenalidomide therapy. (As long as the patient does not exhibit progression, the decision of how many cycles of combination therapy beyond 6 is at the discretion of the treating team and investigator).

Extended dosing of obinutuzumab will begin after combination therapy if patients demonstrate at least stable disease on response assessment. In the extended dosing schedule, obinutuzumab will be administered every 2 months, and in the absence of progression, will be dosed for maximum of 30 months (combination + maintenance).

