5.2.1 Lenalidomide Dose and Schedule

Phase I: In the phase I portion of the study the planned dose of lenalidomide for patients with follicular lymphoma and marginal zone lymphoma (SLL patients not included in phase I portion of study) will be based upon the dose escalation table. (table 1) Patients will receive an oral dose daily on days 2 – 22 followed by 6 days rest (28 day cycle).

Table 3. Dose levels to be tested in phase I portion		
Dose Level	Lenalidomide Dose (days 2-22 followed by 6 days of no therapy)	Obinutuzumab dose
-1	5 mg	1000mg IV
1	10 mg	
2	15 mg	
3	20 mg	

Phase II: Lenalidomide will be administered orally at the maximum tolerated dose (MTD) (as defined by the Phase I portion of the study) on days 2 to 22 of a 28 day cycle in patients with follicular lymphoma and marginal zone lymphoma. Patients with a diagnosis of small lymphocytic lymphoma (SLL) will begin cycle #1 at a maximum dose of 10 mg total daily on days 2 to 22 of a 28 day cycle. This dose will be escalated by 5mg with each cycle up to the MTD if no toxicity is encountered. (see dose modification for lenalidomide table). In the absence of progression or toxicity, patients will remain on lenalidomide treatment for a total of 6-12 months/cycles.

Only one cycle of study drug will be supplied to the patient each cycle.

If a dose of lenalidomide is missed, it should be taken as soon as possible on the same day. If it is missed for the entire day, it should not be made up.

Patients who take more than the prescribed dose of lenalidomide should be instructed to seek emergency medical care if needed and contact study staff immediately. Subjects experiencing adverse events may need study treatment modifications. See Tables 6 and 7.

Supplier

Celgene Corporation will supply Revlimid® (lenalidomide) to study participants at no charge through the Revlimid REMS® program. All physicians who prescribe lenalidomide for research subjects enrolled into this trial and all research subjects enrolled into this trial must be registered in and must comply with all requirements of Celgene's Revlimid REMS® program.

Dosage form

Lenalidomide will be supplied as capsules for oral administration. The capsules are available in 2.5 mg, 5mg and 25mg capsule strengths.

Packaging

Lenalidomide will be shipped directly to the patient. Bottles will contain a sufficient number of capsules for one cycle of dosing.

Storage

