11. STATISTICAL CONSIDERATIONS

This is a single-center, open label, phase I/II study in patients with refractory or relapsed indolent lymphoma. The feasibility of administrating lenalidomide in combination with obinutuzumab and the MTD of the combination will be determined in the phase I part of the study. When the MTD has been established, the efficacy of the combination will be further evaluated in the phase II part of the study in two patient cohorts simultaneously. The two patient cohorts are the patients with follicular lymphoma (grade 1-3a) and the patients with either follicular lymphoma, marginal zone lymphoma, or SLL. A maximum of 72 patients (18 in phase I and 60 in phase II (30 patients each cohort); the patients treated at the MTD in phase I will be counted as the first group of patients treated in phase II) will be enrolled in this study on an intent-to-treat basis.

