11.1 STATISTICAL/STUDY DESIGN

11.1.1 Phase I

The primary objective of the phase I part of the study is to determine the maximum tolerated dose (MTD) of lenalidomide when given in combination with obinutuzumab for subsequent testing in the phase II part of the trial. There are three predefined dose levels for lenalidomide (10 mg, 15 mg, 20 mg) with a fixed dose of obinutuzumab (1000mg) as outlined in Table 2.

Dose limiting toxicity (DLT) will be assessed during the first course of each cohort (28 days), and refers to a medically significant event which meets one of the following criteria using National Cancer Institute Common Terminology Criteria for Adverse Events (NCI CTCAE) version 4:

- Grade 3 or higher non-hematologic AE which is felt to be related to the study drug by the investigator with the exception of the following:
- Transient grade 3 or more infusion reaction that completely resolves within 24 hours.
- Grade 4 hematologic toxicity (Platelet count is defined as <25,000 for the purposes of determining DLT).
- Grade 3 neutropenia with elevated temperature (defined as >= 101 degrees F to be confirmed on two occasions).
- Grade 3 thrombocytopenia with bleeding.
- Treatment delay of greater than 2 weeks due to treatment related toxicity.

The target rate of DLT is 30%. The standard '3+3' design will be used. Applying the 3+3 design, the first cohort of 3 patients will be treated at dose level 1 and evaluated at the end of 28 days. The algorithm is as follows: (1) If 0 out of 3 patients experiences DLT, the next cohort of 3 patients will be

~~2013-0261: Obinutuzumab Plus Lenalidomide in Low Grade Lymphoma~~

treated at the next higher dose level. (2) If 1 out of 3 patients develop DLT, additional 3 patients will be treated at the same dose level. If no more DLT develops at the dose, i.e. 1 out of a total of 6 patients develops DLT, the dose escalation continues for the next cohort of 3 patients. (3) At any given dose, if greater than 1 out 3 patients or 1 out of 6 patients experience DLT, the dose level exceeds the MTD and 3 more patients will be treated at the next lower dose if there are less than 6 patients already treated at that dose. Following the above scheme, MTD is defined as the highest dose level in which 6 patients have been treated with less than 2 instances of DLT. Given 3 dose levels, it is anticipated that up to 18 eligible patients are required for the phase I part of the study.

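### The ceilings of 18 (phase I) and 72 (study) rest on three lenalidomide levels, but Tables 1 and 3 list four; with level -1 in the design the true maxima are 24 and 78

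*Combined protocol and SAP*

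**What the plan says.** Section 11.1.1 fixes the number of levels at three, "There are three predefined dose levels for lenalidomide (10 mg, 15 mg, 20 mg"), and ties the phase I size to it: "Given 3 dose levels, it is anticipated that up to 18 eligible patients are required for the phase I part of the study". Section 2.3.2 gives the same three levels. Section 4.1 does so too, referring to Table 1, and states the size as a limit: "Up to 18 patients may participate in the Phase I component of the study, depending on the level at which toxicity is observed". Section 11 then builds the study total: "A maximum of 72 patients (18 in phase I and 60 in phase II (30 patients each cohort"). Section 2.3.1 carries the same total, and section 11.1.2 explains that the 60 phase II patients are 54 new ones plus 6 already treated at the MTD.

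Table 1 in section 4.1 has four rows: level -1 (5 mg) and levels 1, 2 and 3 (10, 15 and 20 mg). The table in section 5.2.1, headed "Table 3. Dose levels to be tested in phase I portion", repeats all four. In section 11.1.1, "the first cohort of 3 patients will be treated at dose level 1", which is 10 mg. When a level shows too many DLTs, rule (3) there adds three patients one dose down, provided that dose has had fewer than six.

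For the list of levels, section 11.1.1 points to Table 2. Table 2 (section 5.1.4) is the obinutuzumab infusion table.

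**The concern.** The text counts three levels and the tables list four. The starting level is the lowest of the three in the text, so if it fails, rule (3) needs a level beneath it. Only the tables supply one. No section says when level -1 comes into use, and the sample-size sentence leaves it out.

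Two things are at stake. First, the stated ceilings may not cover the design shown in the plan's own tables. Second, the set of levels from which the MTD can be declared, which is the primary phase I objective, should read the same wherever it appears.

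**Working it through.** **Inputs from the documents**

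- Levels in the text: 3 (sections 2.3.2, 4.1, 11.1.1). Levels in the tables: 4 (Tables 1 and 3).
- Start at level 1, cohorts of 3, expansion to 6 after 1 DLT in 3, and step-down only to a level with fewer than 6 patients (section 11.1.1). No level therefore takes more than 6.
- MTD: the highest level with 6 patients treated and at most 1 DLT (section 11.1.1).
- Phase II: 60 patients, of whom 6 come from phase I (section 11.1.2).

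**The plan's own figures**

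- Phase I: 3 levels x 6 = 18.
- Study: 18 + 60 - 6 = 72.

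Both reproduce exactly.

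**With level -1 included**

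- Phase I: 4 levels x 6 = 24.
- Study: 24 + 60 - 6 = 78.

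The written rules allow this path: 0/3 at 10 mg; 0/3 at 15 mg; 1/3 and then at least 2/6 at 20 mg; three more at 15 mg, giving at least 2/6; three more at 10 mg, giving at least 2/6; then six at 5 mg. The total is 6 + 6 + 6 + 6 = 24. These maxima do not depend on the DLT rates.

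**How often 18 would be exceeded**

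The documents give only a 30% target DLT rate, so the true rates are assumptions. It is also assumed that a level with 0/3 and no higher level open to it is filled to 6, as the MTD definition requires.

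To return to 10 mg after escalating and fail there, 10 mg must first show 0/3 and then at least 2/3 in the added three. The same holds for 15 mg. At a 30% rate everywhere:

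- P(0/3) = 0.7^3 = 0.343
- P(1/3) = 3 x 0.3 x 0.49 = 0.441
- P(at least 2/3) = 1 - 0.343 - 0.441 = 0.216
- P(20 mg fails) = 0.216 + 0.441 x 0.657 + 0.343 x 0.216 = 0.580, where 0.657 = 1 - 0.343
- P(all four levels entered) = 0.343^2 x 0.216^2 x 0.580 = 0.0032
- Of these, the path with only 3 patients at 20 mg and 3 at 5 mg totals exactly 18: 0.343^2 x 0.216^4 = 0.0003
- P(more than 18) = 0.0032 - 0.0003 = 0.0029

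Exact enumeration of every path gives:

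| Assumed DLT rate at 5/10/15/20 mg | P(5 mg used) | P(phase I > 18) | P(> 18, given 5 mg used) |
|---|---|---|---|
| 30/30/30/30% | 0.546 | 0.0029 | 0.5% |
| 5/10/20/30% | 0.100 | 0.0006 | 0.6% |
| 10/20/30/40% | 0.321 | 0.0030 | 0.9% |
| 20/30/40/50% | 0.562 | 0.0047 | 0.8% |
| 25/30/35/40% | 0.555 | 0.0041 | 0.7% |

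If 10 mg fails before any escalation, phase I uses 3 or 6 patients there and 3 or 6 at 5 mg, so 6 to 12 in all. If 5 mg then becomes the MTD, it has 6 patients and the study total is 9 + 54 = 63 or 12 + 54 = 66.

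**The case against.** The best defence is that level -1 is a conventional fallback row. It is numbered apart from levels 1 to 3 and left out of the count of escalation levels. On that reading the intent is clear, and section 11.1.1 says only that 18 is anticipated. The arithmetic for three levels is correct, and enrolment is almost never affected.

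Much of this stands, and it rules out several stronger readings that a reader might infer:

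- *That the plan gives two opposing instructions after failure at 10 mg.* It does not. Rule (3) read with Table 1 leads to level -1, and no section says otherwise or bars 5 mg. This is a mismatch in the count and a step left unstated.
- *That 18 and 72 fail whenever 5 mg is used.* They do not. In the scenarios above, more than 99% of the trials that use 5 mg stay within 18.
- *That an MTD of 5 mg would leave lenalidomide reductions undefined in Table 6.* Section 6.2 sets a 5 mg floor and ends lenalidomide for patients who would need less.
- *That failure at every level has no consequence.* It follows from the text: without a level meeting the MTD definition there is no MTD, and sections 2.3.1 and 11 open phase II only once there is one.

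What the defence does not remove is the wording of the limits. Section 4.1 sets an upper bound of 18 and sections 2.3.1 and 11 a maximum of 72. A fallback row left out of the count of levels still has to be included in a maximum.

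**Conclusion.** The point holds as a mismatch between the text and the tables, with ceilings that do not cover the tables' design. If level -1 is part of the design, the maxima are 24 and 78, that is, 6 patients above each stated figure, whatever the DLT rates. If it is not, 18 and 72 are right and the tables are out of step.

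The practical effect is small: the chance of exceeding 18 is about 0.5% or less over the assumed DLT curves. The chance that level -1 is used at all ranges from 0.10 to 0.56 and depends heavily on those assumptions, so it should not be read as a forecast. Severity: minor.

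**What to change.** Reconcile the set of dose levels across sections 2.3.2, 4.1 and 11.1.1 and Tables 1 and 3, and correct the reference to Table 2 in section 11.1.1. Which levels belong in the design is for the sponsor to decide.

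- If level -1 is retained: restate the maxima as 24 and 78 in sections 2.3.1, 4.1, 11 and 11.1.1, wherever each figure appears. Add a sentence making explicit what the text already implies, that no MTD is declared and phase II does not open if no level meets the MTD definition.
- If it is not retained: make both tables match the three-level text. The figures 18 and 72 then stand.

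The cost is wording and, in the first case, two restated numbers. The larger ceiling would rarely be reached.

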11.1.2 Phase II

The primary objective for the phase II part is to further evaluate the safety and efficacy of lenalidomide when given in combination with obinutuzumab at the MTD of lenalidomide determined in phase I. The maximum number of patients that will be recruited for the phase II part is 60 (include additional 54 and the 6 patients treated at the MTD in phase I) with 30 for each of the two patient cohorts: the patients with follicular lymphoma (grade 1-3a) and the patients with either follicular lymphoma, marginal zone lymphoma or SLL. The patients who are treated at the MTD in the phase I part will be included in phase II (in relevant cohort). The objective response (complete response + partial response) after 6 cycles and DLT after 1 cycle will be monitored simultaneously using the Bayesian approach of Thall, Simon, Estey (1995, 1996) as extended by Thall and Sung (1998).

Cohort A: Patients with Follicular lymphoma

Historical data on 43 patients (Witzig, 2009) with relapsed or refractory indolent non-Hodgkin's lymphoma treated with lenalidomide show an objective response (OR) rate of 23% and DLT rate of under 30%. Independence was assumed between OR and DLT. It is expected for the current trial that the two-drug combination will improve the OR rate by 20% to 43% while the DLT rate is maintained at or below 30%. A sample size of 30 patients ensures that, if the trial is not terminated early, a posterior 90% credible interval for OR rate will have width of 0.283 at most, under the assumption of a 43% of OR rate. We will claim that the regimen is worth of further investigation if the lower limit of the posterior 90% credible interval for OR rate is higher than 0.23. The probabilities of OR and DLT for the historical data are modeled by beta distributions (*Beta* (9.89, 33.11) and *Beta* (12.9, 30.1), respectively). The prior probabilities of OR and DLT for the experimental regimen are also modeled by beta distributions (*Beta* (0.46, 1.54) and *Beta* (0.6, 1.4), respectively), which have the same *means* as the corresponding beta distributions for the historical data.

Denoting the historical probabilities of objective response rate and DLT rate by $\{p(\text{OR}, \text{H}), p(\text{DLT}, \text{H})\}$, the following decision criteria will be applied:

- 1) Let E correspond to the experimental treatment, stop if
 $\text{Prob}\{p(\text{OR}, \text{H}) + \delta_{\text{OR}} > p(\text{OR}, \text{E}) \mid \text{data}\} > 0.95$, where $\delta_{\text{CR}} = 0.20$

2) Stop if $\text{Prob}\{p(\text{DLT}, \text{H}) + \delta_{\text{TOX}} < p(\text{DLT}, \text{E}) | \text{data}\} > 0.95$, where $\delta_{\text{DLT}} = 0$

Patients will be monitored in cohorts of 10 according to the following stopping boundaries for overall response and toxicity.

Number of patients evaluated	Recommend stopping if \leq OR observed	Recommend stopping if \geq DLT observed
10	1	7
20	4	11
30	7	15

The operating characteristics are summarized in the following table (based on simulations from 10,000 trials).

True DLT Rate	True OR Rate	Prob(stop the trial early)
0.10	0.13	0.9047
	0.23	0.5420
	0.33	0.2014
	0.43	0.0491
	0.53	0.0082
0.20	0.13	0.9048
	0.23	0.5426
	0.33	0.2025
	0.43	0.0503
	0.53	0.0095
0.30	0.13	0.9069
	0.23	0.5528
	0.33	0.2203
	0.43	0.0715
	0.53	0.0316

0.40	0.13	0.9186
	0.23	0.6087
	0.33	0.3177
	0.43	0.1875
	0.53	0.1526
0.50	0.13	0.9461
	0.23	0.7410
	0.33	0.5485
	0.43	0.4623
	0.53	0.4392

Cohort B: Patients with follicular lymphoma, marginal zone lymphoma or small lymphocytic lymphoma.

Historical data on 44 patients (Ferrajoli, 2008) with relapsed or refractory chronic lymphocytic leukemia treated with lenalidomide show an objective response (OR) rate about 30% and DLT rate of under 30%. Independence was assumed between OR and DLT. It is expected for the current trial that the two-drug combination will improve the OR rate by 20% to 50% while the DLT rate is maintained at or below 30%. A sample size of 30 patients ensures that, if the trial is not terminated early, a posterior 90% credible interval for objective response rate will have width of 0.287 at most, under the assumption of a 50% of objective response rate. We will claim that the regimen is worth of further investigation if the lower limit of the posterior 90% credible interval for OR rate is higher than 0.30. The probabilities of OR and DLT for the historical data are both modeled by beta distributions (*Beta* (13.2, 30.8)) since the historical rates are same for both. The prior probabilities of OR and DLT for the experimental regimen are then also modeled by beta distributions (*Beta* (0.6, 1.4)), which have the same *mean* as the corresponding beta distribution for the historical data.

Denoting the historical probabilities of objective response rate and DLT rate by $\{p(\text{OR}, \text{H}), p(\text{DLT}, \text{H})\}$, the following decision criteria will be applied:

- 1) Let E correspond to the experimental treatment, stop if
 $\text{Prob}\{p(\text{OR}, \text{H}) + \delta_{\text{OR}} > p(\text{OR}, \text{E}) \mid \text{data}\} > 0.95$, where $\delta_{\text{CR}} = 0.2$
- 2) Stop if $\text{Prob}\{p(\text{DLT}, \text{H}) + \delta_{\text{DLT}} < p(\text{DLT}, \text{E}) \mid \text{data}\} > 0.95$, where $\delta_{\text{DLT}} = 0$

Patients will be monitored in cohorts of 10 according to the following stopping boundaries for overall response and DLT.

Number of patients evaluated	Recommend stopping if \leq OR observed	Recommend stopping if \geq DLT observed
10	2	7
20	6	11
30	9	15

The operating characteristics are summarized in the following table (based on simulations from 10,000 trials).

True DLT Rate	True OR Rate	Prob(stop the trial early)
0.10	0.30	0.6491
	0.40	0.3014
	0.50	0.0889
	0.60	0.0164
	0.70	0.0018
0.20	0.30	0.6496
	0.40	0.3023
	0.50	0.0901
	0.60	0.0176
	0.70	0.0031
0.30	0.30	0.6574
	0.40	0.3179
	0.50	0.1104
	0.60	0.0395
	0.70	0.0253

0.40	0.30	0.7002
	0.40	0.4031
	0.50	0.2216
	0.60	0.1596
	0.70	0.1471
0.50	0.30	0.8016
	0.40	0.6050
	0.50	0.4848
	0.60	0.4438
	0.70	0.4355

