1.2.3 CLINICAL EXPERIENCE WITH OBINUTUZUMAB IN NON-HODGKIN'S LYMPHOMA

As of December 2011, clinical data on obinutuzumab are available from four Phase I or II studies (Studies BO20999, BO21003, BO21000, and JO21900) and two

Phase III studies (Studies GAO4753g and BO21004/CLL-11). More than 550 patients with CD20-positive malignant disease have been treated with obinutuzumab.

Results from the aggressive and indolent NHL cohorts in ongoing studies are described below.

1. Study BO20999 (Phase I/II): OBINUTUZUMAB Monotherapy

Patients with Indolent Non-Hodgkin's Lymphoma

Forty patients with relapsed or refractory indolent NHL were randomized to receive obinutuzumab in a low-dose cohort ($n=18$) or a high-dose cohort ($n=22$). The low-dose cohort received obinutuzumab 400 mg on Days 1 and 8 of Cycle 1 and 400 mg on Day 1 of Cycles 2–8 (21-day cycles), and the high-dose cohort received obinutuzumab 1600 mg on Days 1 and 8 of Cycle 1 followed by 800 mg on Day 1 of Cycles 2–8 (21-day cycles). Patients had been pretreated with a median of three prior regimens (range, 1–11), and the majority (38 of 40) had received prior rituximab treatment. More than half of these patients (22 of 40) were considered to be rituximab refractory, and 35% (14 of 40) of all patients had previously received an autologous stem-cell transplant. The best overall response rate in the follicular lymphoma patients was 36% in the low-dose cohort (1/14 CR/CRu, 4/14 PR) and 60% in the high-dose cohort (4/20 CR/CRu, 8/20 PR). (Salles et al. 2011)

The most common adverse event of any grade was infusion-related reaction (IRR; 72% low-dose cohort, 73% high-dose cohort). Fifty-five percent of patients had Grade 3 or 4 adverse events; the most common Grade 3/4 adverse events across cohorts were infections (14%), neutropenia (14%), and IRRs (9%), all in the high-dose cohort.

Patients with Aggressive Non-Hodgkin's Lymphoma

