Forty patients with aggressive NHL were enrolled into the Phase II part of the study. Of these patients with aggressive NHL (25 with DLBCL and 15 with mantle-cell lymphoma [MCL]), 19 were treated in the high-dose cohort (15 with DLBCL and 4 with MCL) and 21 were treated in the low-dose cohort (10 with DLBCL and 11 with MCL). Patients were heavily pretreated (median of three prior therapies), with 63% of patients having not responded to or relapsed within 6 months after a previous rituximab-containing regimen (rituximab refractory). The best overall response rate was 24% in the low-dose cohort (DLBCL: 2 PR, 1 CRu); MCL: 2 CR) and 37% in the high-dose cohort (DLBCL: 3 CR, 2 PR; MCL: 2 PR). (Morschhauser et al. 2011)

The most common adverse event of any grade was IRR (81% low dose cohort, 68% high dose cohort). Grade 3 or 4 adverse events occurring with $\geq 5\%$ frequency were anemia (10%), thrombocytopenia (8%), IRR (8%), tumor lysis syndrome (5%) and cardiac failure (5%). Adverse events did not increase in the high-dose cohort compared to the low-dose cohort. There was one Grade 5

adverse event, cardiorespiratory arrest that was thought to be secondary to ventricular arrhythmia.

b. Study BO21003 (Phase II): Obinutuzumab Monotherapy plus Maintenance

Study BO21003 is an ongoing, open-label, multicenter, randomized, Phase I/II study to investigate the efficacy and safety of obinutuzumab monotherapy compared with that of rituximab monotherapy in patients with relapsed indolent NHL. In the Phase II portion of the study 175 patients (149 follicular, 26 non-follicular) were randomized to receive 4 weekly infusions of obinutuzumab (1000 mg) or rituximab (375mg/m²). Patients without progression continued therapy with obinutuzumab or rituximab every 2 months for 2 years. The ORR at the end of treatment in the follicular lymphoma cohort was 45% for obinutuzumab and 33% for rituximab, as assessed by the investigators. A blinded central review was also performed and the ORR was 45% for obinutuzumab and 27% for rituximab. (Sehn et al. 2011)

More IRRs were reported in the obinutuzumab arm (any grade: 72% vs. 49%, Grade 3/4: 11% vs. 5%, for obinutuzumab and rituximab, respectively). Other AEs of any grade that occurred with \geq 5% frequency with obinutuzumab compared to rituximab were fatigue, cough, back pain, and decreased appetite.

c. Study BO21000 (Phase Ib): Obinutuzumab in Combination with Chemotherapy

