1.4 STUDY RATIONALE

We hypothesize that the high clinical responses noted in indolent lymphoma patients following lenalidomide and rituximab is related to the combination's ability to augment the immune response, and subsequent ADCC through alteration of immune cell subsets in the tumor and peripheral blood. Lenalidomide has been shown to activate NK cells, T cells, or both and leads to expansion of immune effector cells in-vivo in NHL and CLL models. In preclinical models, we have also shown the synergistic anti-tumor effect of combining lenalidomide with anti-CD20 molecules.

As noted above, obinutuzumab is a new, humanized anti-CD20 monoclonal antibody which binds to a unique type II epitope on the cell surface. Obinutuzumab has demonstrated increased affinity to the FCgRIIIa receptor, and may have increased ADCC when compared to rituximab. Preliminary studies also suggest the obinutuzumab is effective in patients with relapsed/refractory indolent lymphoma. (Salles et al 2011)

Combining an anti-CD20 antibody with increased affinity for the FCgRIIIa receptor with a immunomodulatory agent that increases ADCC is rational and has the potential to build upon the anti-lymphoma characteristics of both agents. Both agents are well tolerated, and the expected toxicity profile is mild.

The starting dose of lenalidomide is based upon the initial dose finding study by Wang et al which determined the maximum tolerated dose of lenalidomide with rituximab was 20mg daily in relapsed NHL. Although we do not expect

significant additional toxicity with obinutuzumab the first cohort of patients will be started at dose level 1 (10mg daily) of lenalidomide. (Wang et al 2012)

A unit dose of 1000 mg of GA101 was chosen for studies of NHL after a review of data from completed Phase I studies was undertaken. This unit dose of GA101 to be used in future studies was based on the following findings:

- No dose-limiting toxicities were observed and no maximum tolerated dose was reached in Phase I (doses from 50 mg to 2000 mg were tested).
- Clinical activity (responses) was observed at all dose levels tested.
- PK analyses suggested that a decreased variability of drug exposure related to tumor burden was achieved at doses above 800 mg given on Days 1, 8, 22 and every 3 weeks for nine doses.

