- GA101 was well tolerated with a preliminary safety profile similar to that of rituximab in NHL patients (i.e., mainly Grade 1–2 toxicities, with more frequent IRRs around the time of the first infusion, decreasing with subsequent infusions).

After a comprehensive review of all safety, efficacy, and PK data obtained in Phase I studies, a total GA101 dose of 1000 mg for all infusions was chosen as the dose to be used in future Phase II and Phase III studies by the sponsor since it was the dose most likely to be well tolerated and efficacious in a majority of NHL patients regardless of their initial tumor burden.

In order to coordinate the dosing of study drugs during the first 6 months of treatment, GA101 will be given on 28-day cycles for the first six cycles in this study. On cycle 1 of therapy, the dose of GA101 will be divided over 2 days; day 1, 100mg and Day 2, 900mg. PK modeling suggests that giving additional doses of GA101 on Days 8 and 15 of Cycle 1, and then every 2 months beyond 6 months, will be needed in order to saturate target-mediated clearance achieve and maintain a steady state of drug early and as long as possible during treatment.

After the maximum tolerated dose is found, patients will be enrolled in two cohorts. Prior studies in various B cell malignancies have observed different response profiles in patients with SLL and marginal zone lymphoma compared to patients with follicular lymphoma (Fowler et al).

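### Should the Cohort A success rule, set against lenalidomide alone, be qualified because obinutuzumab alone has a reported response rate of 45%?

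*Combined protocol and SAP*

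**What the plan says.** Section 11.1.2 takes its Cohort A reference from 43 patients with relapsed or refractory indolent lymphoma given lenalidomide, of whom 23% responded. It expects that "the two-drug combination will improve the OR rate by 20% to 43"%, stops for futility against the historical rate plus 0.20, and declares the regimen worth pursuing if, at 30 patients, the "lower limit of the posterior 90% credible interval for OR rate is higher than 0.23". No rate for obinutuzumab alone enters the target, the prior, the boundaries or the rule.

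Section 1.2.3 gives such rates for follicular lymphoma. For the randomised comparison with rituximab it states: "The ORR at the end of treatment in the follicular lymphoma cohort was 45% for obinutuzumab and 33% for rituximab"; blinded central review also gave 45% for obinutuzumab. The antibody dose there was 1000 mg, this trial's unit dose. For the earlier monotherapy study it states: "The best overall response rate in the follicular lymphoma patients was 36% in the low-dose cohort" (5 of 14), and 60% in the high-dose cohort (12 of 20).

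Section 2.2.1 lists safety and overall response rate as the Phase II objectives. Section 11.2 plans a Clopper-Pearson interval for the response rate in each cohort.

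**The concern.** Section 1.4 justifies the pair on the ground that it "has the potential to build upon the anti-lymphoma characteristics of both agents". One would then expect the success criterion to bear on both components. It bears on lenalidomide only, and the target for the combination (43%) is below a rate that the same protocol reports for the antibody by itself (45%). If lenalidomide added nothing, the trial could still declare success, and a reader might take that as evidence for the combination. What is at stake is whether a result of 12 to 14 responses in 30 is over-read.

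**Working it through.** **Inputs.** From 11.1.2, Cohort A: prior Beta(0.46, 1.54), historical Beta(9.89, 33.11), 30 patients, and response futility limits of at most 1 of 10 and at most 4 of 20. From 1.2.3: obinutuzumab alone at 45%, 36% and 60%.

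**Reproducing the plan.** With x responses in 30 the posterior is Beta(0.46 + x, 31.54 − x). At x = 12.9 (43%) the equal-tailed 90% interval runs from 0.2791 to 0.5619, width 0.2828, which matches the stated 0.283. An exact binomial recursion over the looks at 10 and 20 patients gives early-stopping probabilities of 0.9047, 0.5420, 0.2014, 0.0491 and 0.0082 at true response rates of 13%, 23%, 33%, 43% and 53%. These equal the plan's table at a DLT rate of 0.10.

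**Where the rule bites.** The posterior 5th percentile is 0.2259 at 11 of 30 and 0.2536 at 12 of 30. The rule is therefore met at 12 responses (40%) or more.

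**Probability of meeting the rule** (response looks included):

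| True response rate | Probability |
|---|---|
| 23% | 0.027 |
| 36% | 0.384 |
| 43% | 0.689 |
| 45% | 0.762 |
| 50% | 0.895 |
| 60% | 0.990 |

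With the DLT looks at a true DLT rate of 30%, the chance of passing those looks is 0.976, so the 45% entry becomes 0.762 × 0.976 = 0.744.

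**What a marginal pass says about 45%.** Treating 0.45 as fixed, the posterior probability that the rate exceeds it is 0.24 at 12 of 30, 0.36 at 13 and 0.50 at 14. At a true 45% the trial ends with 12 to 14 responses with probability 0.407, which is 0.407 / 0.762 = 53% of the positive results.

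**What the planned reporting already shows.** Section 11.2 does not give the level of its Clopper-Pearson interval. At 12 of 30 the 95% interval is 0.227 to 0.594. It contains 45%, so the reader sees that a marginal pass does not separate the combination from the antibody alone.

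**How firm the 45% is.** The size of the obinutuzumab follicular arm is not given; there were 149 follicular patients over two arms. Assuming 60 to 90, an exact 95% interval around 45% runs from about 32–34% to about 55–58%, so 43% is well inside it. The other two figures are best responses at doses not used here, with exact 95% intervals of 13–65% (5 of 14) and 36–81% (12 of 20).

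**What a rule against 45% would cost.** A posterior lower limit above 0.45 needs 19 of 30 (63.3%). At the 43% target that happens with probability 0.020. Thirty patients in one arm cannot answer that question.

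**The case for a change.** The strongest case for a change is that the 23% reference is just as much a cross-trial figure as the 45%: it comes from 43 patients with mixed indolent histologies. A design that rests on one historical single-agent rate cannot dismiss the other merely for being historical, and every follicular rate for obinutuzumab alone in the protocol (36%, 45%, 60%) exceeds 0.23. One sentence and one descriptive probability would cost almost nothing.

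The facts in this stand. The rule does not address benefit over obinutuzumab, and the plan does not say so. But the remedy gains little. The sentence would disclaim a superiority that the plan never asserts. Saying that a pass shows activity above lenalidomide would itself be too strong: with the plan's own historical beta distribution, rather than a fixed 0.23, the probability that the combination exceeds lenalidomide at 12 of 30 is 0.93, against 0.976 with 0.23 fixed.

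A posterior probability against a fixed 0.45 would ignore the sampling error in that figure and differences in population and timing. The source reports response at end of treatment in relapsed patients, under a schedule of four weekly infusions with continued dosing for those without progression. This trial monitors response after 6 cycles in relapsed or refractory patients. The probability would feed no decision and would largely repeat the planned interval.

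Nor should the 0.76 be read as an error rate. A rule designed around 43% (probability 0.69) will usually be met at 45%.

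**Conclusion.** The observation is correct, but it calls for no change. The Cohort A rule is a screen against one external lenalidomide-alone rate. It does that job: probability 0.03 of being met at 23%, and 0.69 at the 43% target. It does not separate the combination from obinutuzumab alone. If the true rate were 45%, it would be met about three times in four, and over the reported 36% to 60% the probability runs from 0.38 to 0.99. That is the ordinary limit of a single-arm screen whose stated claim is only that further study is warranted, and a fair trade-off at 30 patients. The objectives, sample size, boundaries and rule would all stay as they are, and an analyst reporting the rate with its planned interval would describe the limit without being told to.

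This rests on reading the rule as the go-ahead for further study that the plan states. If a positive result were to be put forward as evidence of added benefit over the antibody, the point would have force. The conclusion is confined to Cohort A: the documents give no obinutuzumab-alone rate for marginal zone lymphoma or SLL, and Section 1.4 notes that prior studies "have observed different response profiles in patients with SLL and marginal zone lymphoma compared to patients with follicular lymphoma".
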